17.1 Adverse Events

All analyses described in Section 17.1 will be based on treatment-emergent adverse events (TEAEs) if not otherwise specified.

TEAEs will be defined according to Table 16.

Table 16: Definition of TEAE

Primary analysis
	
TEAEs will be defined as AEs starting on or after first treatment administration of any IMP (placebo or M2951) until first dose of M2951 during OLE (or until the end of study if the patient declined to participate in OLE period).
 
Only AEs from 12-Week treatment period will be considered.

Final analysis
	
 • For subjects who switch from placebo to M2951 50 mg BID, TEAEs will be defined as AEs starting on or after first treatment administration of M2951 50 mg BID during OLE until the end of study. Only AEs from OLE period will be considered. • For patients who continue with M2951 50 mg BID during OLE, TEAEs will be defined as AEs starting on or after first treatment administration of M2951 during 12-Week double blind treatment period. AEs from both periods (12-Week treatment and OLE) will be considered.

Incomplete AE-related dates will be handled as follows:

- In case the onset date is missing completely or missing partially but the onset month and year, or the onset year are equal to the start of IMP then the onset date will be replaced by the minimum of start of IMP and AE resolution date.
- In all other cases the missing onset day or missing onset month will be replaced by 1.
- Incomplete stop dates will be replaced by the last day of the month (if day is missing only), if not resulting in a date later than the date of subject's death. In the latter case, the date of death will be used to impute the incomplete stop date.
- Further information collected after the cut-off for an analysis (such as a fatal outcome) may be extracted from the Safety data base and presented separately in the CSR.

17.1.1 All Adverse Events

AEs will be coded according to the latest MedDRA version available at the time of analysis. The severity of AEs will be graded using National Cancer Institute - Common Terminology Criteria for Adverse Events (NCI-CTCAE version 4.03) toxicity grades. AEs with missing classification concerning IMP relationship will be considered related to the IMP.

All AEs recorded during the course of the trial (ie assessed from signature of informed consent until the end of the Follow-up/End of Trial visit) will be coded according to the MedDRA and assigned to a SOC and PT.

The number and percentage of subjects experiencing at least one TEAE will be summarized according to MedDRA SOCs and PTs by treatment group, relationship to IMP, and severity. If a subject experiences more than one occurrence of the same TEAE during the trial, the subject will only be counted once for that treatment (the worst severity and the worst relationship to trial treatment will be tabulated).

In case a subject had events with missing and non-missing grades, the maximum of the non-missing grades will be displayed.

A TEAE summary table will include a row for the overall frequency of TEAEs of the following types:

- Any TEAE
- IMP related TEAE
- Serious TEAE
- IMP related serious TEAE
- TEAE with severe intensity (NCI-CTCAE grade ≥ 3 , NCI-CTCAE grade ≥ 4)
- IMP related TEAE with severe intensity (NCI-CTCAE grade ≥ 3 , NCI-CTCAE grade ≥ 4)
- TEAE leading to death
- IMP related TEAE leading to death

A separate TEAE summary table will present the following:

- TEAE leading to interruption of IMP
- IMP related TEAE leading to interruption of IMP
- TEAE leading to withdrawal of IMP
- IMP related TEAE leading to withdrawal of IMP
- TEAE leading to dose reduction
- IMP related TEAE leading to dose reduction
- TEAE leading to study termination
- IMP related TEAE leading to study termination

The TEAE tables to be prepared are listed below.

	Overall frequency	By primary SOC and PT	By PT only
TEAE overview summary	X	NA	NA
TEAE leading to discontinuation of IMP/study/dose reduction of IMP overview summary	X	NA	NA
TEAE by SOC and PT	X	X	
TEAE by PT	X		X
IMP related TEAE by SOC and PT	X	X	
Serious TEAE by SOC and PT	X	X	
IMP related serious TEAE by SOC and PT	X	X	
Non-serious TEAE by SOC and PT*		X	
TEAE by worst grade, SOC and PT		X	
IMP related TEAE by worst grade, SOC and PT		X	
TEAE leading to death by SOC and PT	X	X	
IMP related TEAE leading to death by SOC and PT	X	X	
TEAE leading to withdrawal of IMP by SOC and PT	X	X	
TEAE leading to study termination	X	X	

*A table with all AEs will be first provided and then only AEs exceeding a frequency of 5% in at least one of the treatment groups (> 5%), by SOC and PT will be provided.

Group/SOC terms will be sorted alphabetically. PTs within each group/SOC will be sorted by active dose descending frequency, and alphabetically if multiple PTs have the same frequency.

Pre-treatment and TEAEs will be listed separately by treatment group and subject. Specific data listings of pre-treatment AEs and TEAEs will be performed for subjects with a gap > 4 weeks between 12-Week treatment period and OLE period.

A listing of TEAEs leading to withdrawal of IMP, a listing of TEAEs leading to study termination, if any, will be provided.

Exposure adjusted incidence rates are calculated as number of subjects with AE divided by the sum of the individual times of all subjects in the safety population from start of treatment to first onset of AE. The incidence rate multiplied with 1000 would give the number of AEs expected in 1000 subjects within 1 time unit (for example 1 year). The exposure adjusted incidence rates of TEAEs will be presented by SOC and PT.

17.2 Deaths, Other Serious Adverse Events, and Other Significant Adverse Events

17.2.1 Deaths

A summary of deaths will be provided including (clinicaltrials.gov requirement):

- Number and percentage of (all) deaths
- Number and percentage of the primary cause of death (categories: disease progression, adverse event, unknown, other)

The tabulation of TEAEs leading to death is described in Section 17.1.1. A listing of deaths, if any, will be provided.

In case there is no death in the trial, only the summary of death required by clinicaltrials.gov will be performed, neither tabulation of TEAE leading to death will be edited, nor the listing of death.

17.2.2 Serious Adverse Events

The tabulation of serious TEAEs is described in Section 17.1.1. A subject listing of serious TEAEs will be provided.

17.3 Clinical Laboratory Evaluation

The following laboratory parameters will be measured during the trial as part of the safety evaluation:

- Hematology
- Biochemistry
- Urinalysis
- Coagulation

The clinical laboratory safety tests to be measured in this trial are provided in the protocol (refer to Section 7.4.3 Table 4 of the Clinical Trial Protocol [CTP]).

Continuous protocol-specified clinical laboratory findings (hematology, biochemistry, urinalysis, coagulation) will be summarized by treatment using descriptive statistics (see [Section 11](#)). The statistics will be presented for baseline, each time point during the study, and CFB to each time point, when applicable.

Laboratory results will be classified according to NCI-CTCAE Version 4.03 as provided by the central laboratory. In case a laboratory parameter has bi-directional toxicities (eg Potassium) both directions will be presented for the given parameter (ie Potassium Low and Potassium High). On-treatment values are results of assessments done from the first IMP administration on Day 1. Laboratory results containing a modifier such as “<” or “>=” will be handled case by case for summary statistics and will be reported as collected in the database in subject data listings.

A shift table of baseline versus post-baseline based on the worst NCI-CTCAE grade will be presented by treatment group for hematology and biochemistry.

Additional laboratory results that are neither classified in protocol nor part of NCI-CTCAE will be presented according to the categories based on normal ranges: below normal limits (Low), within normal limits (Normal), and above normal limits (High). Classification into categories will be presented in subject data listings only.

Boxplots of the laboratory values (by treatment arm) by time point will be provided for:

- Hemoglobin
- Absolute reticulocyte count
- White blood cell count
- Absolute neutrophil count
- Absolute lymphocyte count
- Platelet count
- Alanine aminotransferase (ALT)
- Aspartate aminotransferase (AST)
- Gamma-glutamyl transferase (GGT)
- Total bilirubin
- Amylase
- Lipase
- Creatinine
- Blood urea nitrogen (BUN)

Boxplots for laboratory parameters where toxicity grades are defined based on the ratio of the parameter values and the ULN will not be displayed using the unit of measurement but instead using the ratio of the measured value over ULN. This comprises the following parameters:

- ALT
- AST
- GGT
- Total bilirubin
- Creatinine
- Amylase
- Lipase

Listings of individual data with a flag for abnormal values will be provided. Specific data listings of laboratory data will be performed for subjects with a gap > 4 weeks between 12-Week treatment period and OLE period.

Laboratory values that are outside the normal range will also be flagged in the data listings, along with corresponding normal ranges. Any out-of-range hematology, biochemistry, urinalysis and coagulation values that are identified as being clinically significant (ie, values classified as low or high based on normal range and/or value with grade ≥ 1) will be shown in a data listing.

17.4 Vital Signs

Vital signs (body temperature (°C), SBP (mmHg), DBP (mmHg), respiratory rate (breaths/min) and pulse rate (beats/min)) will be summarized by treatment group using descriptive statistics (see Section 11) for baseline, each applicable time point and CFB to each time point.

Body temperature, SBP, DBP, respiratory rate and pulse rate will be analyzed with shift tables of maximum CFB using the categories defined in Table 17:

Table 17: Vital signs categories

Parameter	Unit	Shift	Baseline categories	Post-baseline categories (absolute change)
Temperature	°C	Increase	<37 / ≥ 37 - <38 / ≥ 38 - <39 / ≥ 39 - <40 / ≥ 40	$\leq 0^*$ / >0 - <1 / ≥ 1 - <2 / ≥ 2 - <3 / ≥ 3
Pulse rate	bpm	Increase and decrease	<100 / ≥ 100	$\leq 0^*$ / >0 - ≤ 20 / >20 - ≤ 40 / >40
SBP	mmHg	Increase and decrease	<140 / ≥ 140	$\leq 0^*$ / >0 - ≤ 20 / >20 - ≤ 40 / >40
DBP	mmHg	Increase and decrease	<90 / ≥ 90	$\leq 0^*$ / >0 - ≤ 20 / >20 - ≤ 40 / >40
Respiratory rate	breaths/min	Increase and decrease	<20 / ≥ 20	$\leq 0^*$ / >0 - ≤ 5 / >5 - ≤ 10 / >10

* This category will include the subjects with no changes or decrease/increase in the increase/decrease part of the table respectively.

A listing of maximum CFB and a listing of all vital signs data will be provided.

17.5 12-Lead Electrocardiogram (ECG)

The 12-lead ECG data will be listed and summarized for observed values and CFB values by treatment group using descriptive statistics:

- Ventricular rate (beats/min)

- Pulse rate interval (msec)
- QRS (msec)
- QT (msec)
- Fridericia corrected QT (QTcF) (msec).

QTcF values will be categorized according to their calculated values into the categories

- ≤ 430 msec,
- $> 430 - 450$ msec,
- $> 450 - 480$ msec,
- $> 480 - 500$ msec,
- > 500 msec

and categorized according to their CFB into the categories

- ≤ 30 msec,
- $> 30 - 60$ msec,
- > 60 msec.

The ECG outlier values will also be tabulated. The categories described above will be summarized by treatment group in frequency tables using number and percentage of subjects.

A listing of ECG quantitative values, morphological and rhythm results will be produced.

A shift table of rhythm results, from baseline to end of treatment, of the number and percentage of subjects for each category (Sinus rhythm, Atrial fibrillation, Other, Missing and Total) will be provided. This table will only be performed for the primary analysis.

A shift table of morphological assessments, from baseline to end of observation, of the number and percentage of subjects for each interpretation category (Normal, Abnormal, Missing, and Total) will also be provided, the end of observation referring to the last available observation of the 12-week treatment period for the primary analysis and the last available observation of the study for the final analysis.

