7.4.4.2 Physical Examinations

Physical examinations will be assessed as indicated in [Table 1](#). Physical examination includes assessment of the following: general appearance, skin, head and neck, mouth, lymph nodes, thyroid, abdomen, and musculoskeletal, cardiovascular, and respiratory systems. Physical examination findings during Screening will be recorded as medical history events and findings during the trial as AEs.

7.4.4.3 12-Lead ECG and Chest X-Ray

A 12-lead ECG will be performed during Screening, predose on Day 85, Month 1 of OLE, and Month 6 of OLE. The 12-lead ECG recordings will be obtained after 10 minutes of rest in a semi-supine position.

The following ECG parameters will be obtained directly from the computerized 12-lead ECG recordings: rhythm, ventricular rate, PR interval, QRS duration, and QT interval. The corrected QT interval will be calculated using Fridericia's formula. The overall evaluation (normal/abnormal) will be recorded on the eCRF, and if abnormal, the specific abnormality will be recorded. Abnormal evaluations will be judged as clinically significant or not clinically significant by the Investigator.

The printout of the ECG is to be signed, dated, and filed in the Investigator's Site File along with a signed and dated copy (if the printouts are not on archive-quality paper).

Posterioanterior CXRs will be performed during Screening according to local standard practice. Subjects who had a CXR performed for clinical reasons within 3 months prior to Day 1 do not need to have the CXR repeated. The CXR should show no evidence of active infective process, or any other clinically significant abnormalities. The overall evaluation (normal/abnormal) will be recorded on the eCRF, and if abnormal, the specific abnormality will be recorded. Abnormal evaluations will be judged as clinically significant or not clinically significant by the Investigator.

The 12-lead ECG and CXR will be performed and read locally.

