In all subject data listings, imputed values will be presented. In all listings imputed information will be flagged. Non imputed partial dates will be presented in a format such as “____YYYY”. Where imputation is defined, an imputed date with flag (ie, D for day, M for month) will be reported.

Missing statistics, eg when they cannot be calculated, should be presented as ‘nd’ (denoting “not done”). For example, if n=1, the measure of variability (SD) cannot be computed and should be presented as ‘nd’.

In case of zero records, an empty output with 0 occurrences, or a sentence mentioning that there are no data, will be presented. For tables of AEs and Deaths (outputs required for EudraCT and/or clinicaltrial.gov), if there are no observations, the output must contain the first line ‘Subject with...’ or ‘Subject who died’ displayed with 0 occurrence.

If the System Organ Class (SOC) or Anatomical Therapeutic Class (ATC) term is missing/not coded yet, then 'Uncoded SOC' (or 'Uncoded ATC') will be indicated at the ADaM level. When a Preferred Term (PT) is missing, it will be set to 'Uncoded PT: verbatim text'.

Treatment day:

Treatment day is defined as relative day to the start date of treatment. Treatment day will be calculated accordingly, ie:

- For primary analysis, treatment day 1 is defined as the date of first administration of any IMP.
- For final analysis, treatment day 1 is defined as the first administration of M2951:
 - For subjects who switch from placebo to M2951, the treatment day 1 will be defined as the first administration of M2951 in OLE period
 - For subjects who have taken M2951 during 12-Week treatment period and continue with the same treatment during OLE, the treatment day 1 will be defined as the first administration of M2951 during 12-Week treatment period

The day before is defined as Treatment day -1 (no Treatment day 0 is defined).

Repeated and unscheduled measurements:

Data collected at unscheduled visits will be included and analyzed for safety analyses in the same fashion as the data collected at scheduled visits. Unscheduled measurements will also be used for shift tables.

Gap between 12-Week treatment period and OLE period

Subjects with a gap strictly greater than 4 weeks between 12-Week treatment period and OLE period will be analyzed the same way as subjects without a gap. Specific data listings on safety data (AEs and all laboratory data) will be produced for these subjects for the final analysis.

Time windows

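### The final-analysis ECG morphology shift table uses only the last tracing, and there is no final-analysis rhythm shift table, so transient on-drug ECG changes in the extension can go uncounted

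*SAP*

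**What the plan says.** SAP 17.5 (12-Lead Electrocardiogram) plans two ECG shift tables.

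- **Morphology** (Normal/Abnormal) runs from baseline to end of observation, defined as "the last available observation of the 12-week treatment period for the primary analysis" and "the last available observation of the study for the final analysis".
- **Rhythm** is described as "A shift table of rhythm results, from baseline to end of treatment", with the restriction "This table will only be performed for the primary analysis".

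Other safety shifts follow a different rule. SAP 17.3 plans "A shift table of baseline versus post-baseline based on the worst NCI-CTCAE grade" for hematology and biochemistry. In SAP 17.4, vital signs "will be analyzed with shift tables of maximum CFB using the categories defined in Table 17". SAP Section 11 adds a general rule: "Unscheduled measurements will also be used for shift tables".

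Protocol 7.4.4.3 places the ECGs at Screening and then "predose on Day 85, Month 1 of OLE, and Month 6 of OLE". Under SAP Table 15, the final analysis uses both periods for M2951/M2951 subjects. For Placebo/M2951 subjects it uses data from the extension onward, including after it.

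**The concern.** A shift to the last value shows what the final ECG looked like. A safety reader usually wants to know who developed an abnormality while on drug. The two questions have the same answer only if abnormalities persist or there is a single post-baseline tracing. In the extension there is more than one, and the SAP gives no reason for treating ECGs differently from laboratory values and vital signs.

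Protocol 3.1 lists atrial fibrillation among the important potential risks. It can be intermittent, so a summary that depends on the final tracing, or no rhythm summary at all, suits it poorly. Adverse event tables are only a partial safeguard. Under Protocol 7.4.1.1 an abnormal ECG finding becomes an adverse event only if it is accompanied by symptoms or signs, leads to discontinuation, or is judged medically important.

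**Working it through.** The plan states no figure on this point, so there is none to reproduce. The check is a count of tracings, followed by an illustration.

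**Step 1. Scheduled post-baseline ECGs available to each table.** Inputs are the ECG schedule (Protocol 7.4.4.3), the End of Treatment Visit that replaces Day 85 after early discontinuation (Protocol 7.1.2.1), the data selection in SAP Table 15, and the baselines in SAP Table 2. For Placebo/M2951 subjects the final-analysis baseline is the last value before the first M2951 dose, so the predose Day 85 ECG is baseline and not follow-up.

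| Table | Scheduled post-baseline ECGs | Used | Left out |
|---|---|---|---|
| Primary, morphology and rhythm, either arm | 1 (Day 85 or early End of Treatment) | 1 | 0 |
| Final, morphology, Placebo/M2951 completers | 2 (extension Months 1 and 6) | 1 | 1 |
| Final, morphology, M2951/M2951 completers | 3 (Day 85, extension Months 1 and 6) | 1 | 2 |
| Final, rhythm | no shift table planned | – | – |

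This step needs no assumption. A subject with a normal baseline, abnormal at Month 1 and normal at Month 6, appears as Normal to Normal.

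**Step 2. Unscheduled tracings.** SAP Section 11 admits them to shift tables. Under a last-value rule, an abnormal unscheduled ECG followed by a normal one has no effect on the morphology table. A normal repeat after an abnormal Day 85 tracing, but before the extension starts, would replace it. For rhythm, SAP 17.5 does not say how several tracings are resolved into one end-of-treatment result. In the primary analysis this is the only route by which an on-treatment abnormality could be lost.

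**Step 3. Illustration of size.** These assumptions are not in the documents: normal baseline, each tracing abnormal with probability q, tracings independent, and abnormalities fully transient. With k tracings:

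- any abnormal = 1 − (1 − q)^k
- shown by the last-value table = q
- share of affected subjects missed = 1 − q / [1 − (1 − q)^k]

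| q | Any of 2 | Missed, k = 2 | Any of 3 | Missed, k = 3 |
|---|---|---|---|---|
| 0.02 | 4.0% | 49.5% | 5.9% | 66.0% |
| 0.05 | 9.8% | 48.7% | 14.3% | 64.9% |
| 0.10 | 19.0% | 47.4% | 27.1% | 63.1% |

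**Step 4. Allowance for the primary table.** The Day 85 ECG of an M2951/M2951 subject is also counted in the primary-analysis morphology table, against the same baseline. Taking scheduled ECGs only, the share of affected subjects shown in neither table is 1 − [1 − (1 − q)^2] / [1 − (1 − q)^3]:

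- q = 0.02: 1 − 0.0396/0.0588 = 33%
- q = 0.05: 1 − 0.0975/0.1426 = 32%
- q = 0.10: 1 − 0.190/0.271 = 30%

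Across the two analyses, then, the only scheduled on-drug tracing that a completer loses is extension Month 1.

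**The case against.** The strongest case against has four parts.

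- **The randomized comparison is essentially untouched.** With one scheduled post-baseline ECG, last equals worst. This stands, apart from unscheduled tracings.
- **No scheduled arrhythmia is miscounted.** A reader might infer that atrial fibrillation in the extension will be tabulated as sinus to sinus. The documents do not support that: the rhythm table is confined to the primary analysis. The gap in the extension is a missing table, not a wrong cell.
- **The findings are not hidden from the report.** SAP 17.5 plans a listing of all morphology and rhythm results, QTcF categories and tabulated outliers. Protocol 8.5.5 provides for clinically noteworthy ECG findings to be listed and summarized as appropriate. This stands, but a listing gives no count by group, the defined categories cover QTcF only, and the protocol wording commits to no specific rhythm or morphology table.
- **A worst-value rule has its own distortion.** With no true difference and q = 0.05, the final-analysis columns would read 14.3% against 9.8%, simply because one group has three tracings and the other two. Locally read Normal/Abnormal calls without a clinical-significance qualifier would also pick up trivial variants. Both are fair and argue for adding the worst-value display with a footnote, not for replacing the existing one.

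**Conclusion.** The point holds for the uncontrolled final analysis. For completers the morphology shift table discards two of three scheduled post-baseline tracings (M2951/M2951) or one of two (Placebo/M2951), contrary to the SAP's own practice for laboratory and vital-sign shifts. There is also no final-analysis rhythm shift table for a safety question that includes atrial fibrillation. In the primary analysis only a subject with an unscheduled ECG could be affected.

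A reader might infer that the plan conceals roughly two thirds of ECG toxicity on M2951. That does not follow. The 63% to 66% figure applies to one table and assumes independent, fully transient abnormalities at invented rates. Allowing for the primary table brings it to 30% to 33%, and full persistence brings it to zero. The figures describe Normal/Abnormal morphology, not atrial fibrillation. The tracing counts are the firm part; every percentage is illustrative. This is a worthwhile, inexpensive improvement to a safety display and does not threaten the trial's main conclusions.

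**What to change.** Amend SAP 17.5 as follows.

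1. In the final-analysis morphology output, add a shift from baseline to worst post-baseline result (any abnormal) within the analysis period, including unscheduled ECGs. Keep the last-observation version beside it.
2. Apply the same worst-result rule to the primary morphology and rhythm tables where unscheduled ECGs exist, and state how several tracings are resolved. For rhythm, declare the ranking in advance, for example atrial fibrillation, then other, then sinus.
3. Produce the rhythm shift table for the final analysis on the same worst-result basis.
4. Footnote the final-analysis worst-result tables to say that M2951/M2951 subjects contribute up to three scheduled tracings and Placebo/M2951 subjects up to two, so the columns are not directly comparable.

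The cost is a short SAP amendment and minor programming before the relevant database lock; no new data are collected. The downside is that worst-case counts rise with the number of tracings, a property the SAP already accepts for laboratory and vital-sign shifts.
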